8.7.2. Banked Biospecimens for Genetics

A 4-mL blood sample optimized for DNA isolation (Prep D1) will be collected as local regulations and IRBs/ECs allow.

Banked Biospecimens may be used for research related to the study intervention(s) and cancer. Genes and other analytes (eg, proteins, RNA, nondrung metabolites) may be studied using the banked samples.

See [Appendix 5](#) for information regarding genetic research. Details on processes for collection and shipment of these samples can be found in the laboratory manual.

8.8. Biomarkers

Biospecimens collected for pharmacodynamic and other biomarker assessments will include peripheral blood, and tumor tissues which will be used to analyze DNA, RNA, and proteins, for achieving planned biomarker objectives. Refer to the [SoA](#) for sample collection time points and Study/Laboratory Manual for sample processing and shipping. The following biospecimen types are planned to be collected in support of study objectives. Additional biospecimens collected over the course of participant disease management may be submitted for biomarker analyses.

8.8.1. Archival/De Novo Tumor Biopsies

Tumor biospecimens from archival FFPE or de novo biopsies will be used to analyze candidate nucleic acid and protein biomarkers for their ability to identify those participants who are most likely to benefit from treatment with the study drugs. Biomarkers may include, but are not limited to target expression, nucleic acid analyses, as well as cell types and constituents of the TME. De Novo tumor biopsies obtained upon disease progression may be used to investigate pharmacodynamic activities, mode of action and acquired mechanisms of resistance. **CC1**

[REDACTED]. Additional information on tissue collection procedures can be found in the Laboratory/Study Manual.

Pre-treatment archival FFPE material containing tumor that is of diagnostic quality and representative of the diagnosed malignancy collected at least one year prior to study start is required of all participants, and if not available, a pre-treatment de novo (fresh) tumor biopsy will be required. If the archival sample is older than 1 year and a biopsy during screening cannot be performed, the investigator must contact the sponsor to discuss eligibility prior to enrollment.

For 10-15 participants in Part 2, a de novo tumor biopsy at pre-treatment [REDACTED] will be required. An archival sample collected prior to study start may not be substituted for the mandatory pre-treatment paired biopsy in Part 2 dose

expansion. For all other participants, [REDACTED] biopsy is optional but highly encouraged. However, if participants agree to provide fresh on-treatment tumor biopsies then they will also need to provide fresh pre-treatment tumor biopsies as paired samples. Tumor paired biopsies should preferably be taken from the same lesion and from a lesion that has not been previously irradiated. Tumor tissue from cytologic sampling (eg, fine needle aspiration, including FFPE cell pellet material) or bone specimen, is not adequate and should not be submitted.

Participants should not be subjected to a significant risk procedure to obtain the biopsies (ie, the absolute risk of mortality or major morbidity in the participant's clinical setting and at the institution completing the procedure should be <2%).

Additional information on tissue collection procedures can be found in the Laboratory Manual.

8.8.2. Whole Blood, Plasma, Serum

Peripheral blood and derivatives may be used to characterize cell [REDACTED] genotypes, measure soluble proteins and analyze nucleic acids to support study objectives. [REDACTED]

[REDACTED]. We will also collect whole blood samples for DNA sequencing to detect germline mutations to serve as a nonnal control for detecting somatic mutations. Additional analyses may be warranted based on emerging data. Should the site require cytokine information for participant management such as in the case of suspected CRS, the site should collect an additional blood sample for local analysis.

CCl [REDACTED]

CCl [REDACTED]

[REDACTED] in the SoA. Instructions for sample collection, processing, storage shipment and detailed panels of cytokine/chemokine and immunophenotyping markers will be provided in the laboratory manual.

8.9. Immunogenicity Assessments

Blood samples will be collected for determination of ADA and NAb as specified in the SoA. Instructions for the collection and handling of biological samples will be provided in the laboratory manual or by the sponsor. The actual date and time (24-hour clock time) of each sample will be recorded.

Samples collected for determination of ADA and NAb may also be used for additional characterization of the immune response and/or evaluation of the bioanalytical method, or for other internal exploratory purposes. These data will be used for internal exploratory purposes and not reported in CSR.

Genetic analyses will not be performed on these samples. Participant confidentiality will be maintained.

Samples will be analyzed using a validated analytical method in compliance with applicable SOPs. Samples determined to be positive for ADA may be further characterized for neutralization activity.

The immunogenicity samples must be processed and shipped as indicated in the instructions provided to the investigator site to maintain sample integrity. Any deviations from the immunogenicity sample handling procedure (eg, sample collection and processing steps, interim storage, or shipping conditions), including any actions taken, must be documented and reported to the sponsor. On a case-by-case basis, the sponsor may make a determination as to whether sample integrity has been compromised.

Any changes in the timing or addition of time points for any planned study assessments must be documented and approved by the relevant study team member and then archived in the sponsor and site study files, but will not constitute a protocol amendment. The IRB/EC will be informed of any safety issues that require alteration of the safety monitoring scheme or amendment of the ICD.

8.10. Health Economics

Health economics/medical resource utilization and health economics parameters are not evaluated in this study.

9. STATISTICAL CONSIDERATIONS

Detailed methodology for summary and statistical analyses of the data collected in this study is outlined here and further detailed in the SAP, which will be maintained by the sponsor. The SAP may modify what is outlined in the protocol where appropriate; however, any major modifications of the primary endpoint definitions or their analyses will also be reflected in a protocol amendment.

The data will be summarized with respect to demographic and baseline characteristics, efficacy observations and measurements, safety observations and measurements, pharmacokinetic and biomarker measurements.

9.1. Statistical Hypotheses

There is no formal hypothesis testing in this study.

9.2. Sample Size Determination

The total number of participants is estimated to be approximately 74-172 enrolled to study intervention.

9.2.1. Part 1: Dose Escalation

Approximately 14-22 participants are expected to be enrolled in Part 1 dose escalation. The total number of participants will depend on the number of dose levels needed to determine

the MTD/RP2D and the actual number of participants evaluable for DLT at each dose level. In general, each cohort in the dose escalation part will be approximately 2-4 participants. For the dose level that is estimated to be the MTD, a minimum of 6 evaluable participants will be treated at this dose.

9.2.2. Part 2: Dose Expansion

Each cohort in Part 2 will enroll 20-30 participants. Approximately 60-90 participants will be initially enrolled in the first three cohorts, with the option to further enroll approximately 40-60 participants in an additional two cohorts.

Clinical response will be continuously monitored in each expansion cohort and if no clinical benefit is observed enrollment may be stopped for the respective cohort.

A Beta-Binomial model, using a non-informative prior (ie, Jeffery's prior), was used to estimate the posterior probability that the true ORR is $\leq 10\%$, $> 20\%$, or $> 30\%$ based on an observed ORR. Enrollment of participants into a given cohort may be discontinued if minimal or no anti-tumor activity (eg, 0 or 1 response) is observed in the first 10 evaluable participants. For example, if 1 out of 10 participants have tumor response, this would translate into a posterior probability equal to 0.77 that the true response is inferior to 20%. Alternatively, if 5 out of 20 participants have tumor response, this would translate into a posterior probability equal to 0.725 that the true response is not inferior to 20%. The results for observed response rates ranging from 20-40% with 20 or 30 participants per expansion cohort are provided in Table 5. Posterior probabilities may be calculated by using informative priors based on the anti-tumor activity that may be observed during dose escalation. These posterior probabilities will be assessed for each indication during Part 2 when at least 10 participants have been enrolled in a given indication/subgroup.

Table 5. Posterior Probability that the true ORR (θ) is above or below some threshold, for a given observed ORR.

Observed ORR	$P(\theta \leq 10\% \text{data})$	$P(\theta > 20\% \text{data})$	$P(\theta > 30\% \text{data})$
4/20 (20%)	0.078	0.523	0.165
5/20 (25%)	0.023	0.725	0.323
6/20 (30%)	0.005	0.866	0.513
7/20 (35%)	0.001	0.946	0.696
8/20 (40%)	0	0.982	0.836
6/30 (20%)	0.044	0.519	0.113
7/30 (23%)	0.014	0.689	0.216

Table 5. Posterior Probability that the true ORR (θ) is above or below some threshold, for a given observed ORR.

Observed ORR	$P(\theta \leq 10\% \text{data})$	$P(\theta > 20\% \text{data})$	$P(\theta > 30\% \text{data})$
8/30 (27%)	0.004	0.822	0.354
9/30 (30%)	0.001	0.91	0.511
10/30 (33%)	0	0.96	0.663
11/30 (37%)	0	0.984	0.79
12/30 (40%)	0	0.994	0.882

9.3. Analysis Sets

1. Full analysis set.

The full analysis set includes all enrolled participants.

"Enrolled" means a participant's, or their legally authorized representative's, agreement to participate in a clinical study following completion of the informed consent process. Potential participants who are screened for the purpose of determining eligibility for the study, but do not participate in the study, are not considered enrolled, unless otherwise specified by the protocol.

2. Safety analysis set.

The safety analysis set includes all enrolled participants who receive at least one dose of study intervention. Unless otherwise specified, the safety analysis set will be the default analysis set used for all analyses.

3. Per protocol analysis set (evaluable for MTD).

The per protocol analysis set includes all enrolled and evaluable participants who had at least one dose of study treatment and either experienced DLT or do not have major treatment deviations during the DLT observation period.

4. mITT Population.

The mITT is the analysis population that will follow the ITT principle and include participants receiving at least 1 dose of study medication with baseline assessment and at least 1 post baseline assessment, disease progression, or death before the first tumor assessment. The mITT population may be used for interim analysis and conference presentations when the study is still ongoing.

5. PK analysis sets.

The PK parameter analysis population is defined as all enrolled participants treated who do not have protocol deviations influencing PK assessment, and have sufficient information to estimate at least 1 of the PK parameters of interest.

The PK concentration population is defined as all enrolled participants who are treated and have at least 1 postdose analyte concentration.

6. Response Evaluable Set.

The response evaluable population will include all participants who received at least one dose of study treatment and had baseline disease assessment and at least one post baseline disease assessment.

7. PD/Biomarker analysis set(s).

The PD/Biomarker analysis population is defined as all enrolled participants with at least 1 of the PD/Biomarkers evaluated at pre and/or post dose.

8. Immunogenicity analysis set.

The immunogenicity analysis set includes all enrolled participants who receive at least one dose of study treatment and have at least one sample tested for ADA.

9.4. Statistical Analyses

The SAP will be developed and finalized before any analyses are performed and will describe the analyses and procedures for accounting for missing, unused, and spurious data. This section is a summary of the planned statistical analyses of the primary and secondary endpoints.

Unless otherwise specified, summaries will be presented by dose group and overall. Descriptive statistics, such as the mean, standard deviation, coefficient of variation, median, minimum, and maximum values, will be provided for continuous endpoints. The rates of binary endpoints will be provided along with the corresponding 2-sided 95% confidence intervals using an exact method. Time-to-event endpoints will be summarized using the Kaplan-Meier method and displayed graphically when appropriate. Median event times and 2-sided 95% confidence intervals for each time-to-event endpoint will be provided.

9.4.1. Maximum Tolerated Dose Determination

Determination of MTD will be performed using per protocol analysis set (evaluable for MTD).

Bayesian adaptive approach:

The dose escalation in the Part 1 of the study will be guided by a Bayesian analysis of DLT data for PF-07209960. Dose toxicity is modelled using two-parameter logistic regression for the probability of a participant experiencing a DLT at the given dose.

Assessment of Participant Risk:

After each cohort of participants, the posterior distribution for the risk of DLT for new participants at different doses of interest for PF-07209960 will be evaluated. The posterior distributions will be summarized to provide the posterior probability that the risk of DLT lies within the following intervals:

Under-dosing	[0, 0.16]
Targeted dosing	[0.16, 0.33]
Overdosing	[0.33, 1]

The EWOC principle:

Dosing decisions are guided by the escalation with overdose control principle ([Rogatko et al, 2007](#)). A dose may only be used for newly enrolled participants if the probability of overdosing at that dose is **CCI**.

Recommendation from the BLRM, along with safety (AEs, SAEs), laboratory, PK, biomarker and other relevant data, will be used at the time of each dose escalation and for MTD/RP2D determination.

Prior distributions:

Weakly informative prior distributions based on pre-clinical/expert opinion information will be chosen for the logistic parameters, see [Appendix 8](#).

Starting dose:

The starting dose is **CCI** in Part 1 Dose Escalation. For this dose the prior risk of overdosing satisfies the EWOC criterion.

9.4.1.1. Stopping Criteria

The dose escalation will be stopped when the following criteria are met:

- At least 6 participants have been treated at the recommended MTD/RP2D.
- The dose d^\sim satisfies 1 of the following conditions:
 - The probability (π) of target toxicity at dose d^\sim exceeds 50%, ie, $\Pr(0.16 \leq rr_{d^\sim} < 0.33) \geq 50\%$.
 - A minimum of 15 participants have been treated in the trial.

In case all doses explored appear to be overly toxic and the MTD cannot be determined, the dose escalation will stop.

In case of change of the dosing regimen, DLT data accumulated during the dose escalation with the original regimen might be used to form a MAP prior for further BLRM analysis. MAP priors are derived from hierarchical models, which take into account possible

differences between the studies. Details of priors and general description of MAP approach is presented in [Appendix 8](#) and a statistical technical supplement.

To mitigate the risk of misclassifying DLTs, a sensitivity that uses weighted DLT/AE data (in equivocal cases) within the BLRM will be performed. If all investigators and the sponsor agree on the equivocal DLT/AE data, the DLT weighting approach could be the primary dose escalation method (see [Appendix 8](#)).

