seropositive participants, who are in good health and at low-risk for AIDS-related outcomes, may qualify for inclusion in the study after discussion with the sponsor, but AIDS is exclusionary.

6. Anticoagulation with vitamin K antagonists is not allowed. Anticoagulation with low molecular weight heparin and Factor Xa inhibitors or use of antiplatelet therapy is allowed but must be held per institutional requirements for biopsies and whenever platelet count is $<50,000/\text{mm}^3$. If participants are on antiplatelet therapy, they must be able to hold antiplatelet therapy for first week of study treatment without significantly increased risk of cardiovascular events.
7. AEs from prior therapy which have not recovered to Grade ≤ 1 or baseline.
8. History of Grade ≥ 3 immune-related AE considered related to prior immune modulatory therapy and required immunosuppressive therapy (except endocrine irAEs managed by hormone replacement therapy).
9. Active autoimmune disease that might deteriorate when receiving an immunostimulatory agent. Patients with diabetes type I, vitiligo, psoriasis, or hypo- or hyperthyroid disease not requiring immunosuppressive treatment are eligible.
10. Current use of immunosuppressive medication at the time of randomization, EXCEPT for the following: a) intranasal, inhaled, topical steroids, or local steroid injection (eg, intra-articular injection); b) Systemic corticosteroids at physiologic doses $\leq 10 \text{ mg/day}$ of prednisone or equivalent; c) Steroids as premedication for hypersensitivity reactions (eg, CT scan premedication).
11. Active bleeding disorder in the past 6 months prior to planned first dose.
12. History of interstitial lung disease or pneumonitis.
13. Pregnancy or breastfeeding.

Number of Participants

The total number of participants enrolled to study intervention is estimated to range from approximately 74 to 172.

Part 1 Dose Escalation:

Approximately 14-22 participants are expected to be enrolled in Part 1 dose escalation. The total number of participants will depend on the number of dose levels needed to determine the MTD/RP2D and the actual number of participants evaluable for DLT at each dose level. In general, each cohort in the dose escalation part will be approximately 2-4 participants. DLT observation period is 28 days after C1D1 for all participants. For the dose level that is estimated to be the MTD, a minimum of 6 DLT evaluable participants will be treated at this dose.

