4.3.3. Dose Limiting Toxicity Definition

For the purpose of dose escalation, any of the following AEs will be classified as DLTs:

- Occur in the first cycle of treatment, or within 28 days after the start of the study treatment; and
- Are at least possibly related to PF-07209960; A participant is classified as DLT evaluable if he/she experiences a DLT or if he/she otherwise in the absence of a DLT receives 2 doses of the study intervention during Cycle 1 and has received all scheduled safety assessments during the DLT window. If a participant fails to meet these criteria, he/she may be replaced. Monitoring for DLTs will occur during Part 1.

Significant AEs considered to be related to the study intervention or treatment under investigation that occur after the DLT observation period will be reviewed in context of all safety data available. That review may result in re-evaluation of the dosing level or regimen.

Hematologic DLTs:

1. Grade 4 neutropenia (absolute neutrophil count [ANC] <500/mm³) lasting >7 days;
2. Febrile neutropenia (defined as an ANC <1000/mm³, with a single temperature of >38.3°C [101°F], or a sustained temperature of ≥38°C [100.4°F] for more than one hour);
3. Neutropenic infection (defined as an ANC <1000/mm³ with Grade ≥3 infection);
4. Grade 3 thrombocytopenia (platelet count <50,000 mm³) with any bleeding;
5. Grade 4 thrombocytopenia (platelet count <25,000/mm³);
6. Grade 4 anemia (life-threatening consequences; urgent intervention indicated).

Non-Hematologic DLTs:

- Any Grade ≥3 non-hematologic treatment related AE is a DLT with the following exceptions:
 1. Grade 3 nausea, vomiting, diarrhea, or fatigue that can be controlled with or without medical therapy to Grade ≤2 within 72 hours;
 2. Grade ≥3 laboratory abnormalities without a clinical correlate and that do not require medical intervention, or are corrected to Grade ≤2 with supplementation/appropriate management within 72 hours;

Immune-related AE (irAE) that meet the following criteria:

1. Grade 4 irAE regardless of duration (for lab abnormalities without clinical correlate and do not require medical intervention please refer to criteria above);

2. Grade ≥ 3 colitis regardless of duration (diagnosis of colitis must be supported by diagnostic testing);
3. Grade ≥ 3 non-infectious pneumonitis regardless of duration;
4. Grade 2 non-infectious pneumonitis that does not resolve to \leq Grade 1 within 72 hours of the initiation of maximal supportive care;

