4. ANALYSIS SETS (POPULATIONS FOR ANALYSIS)

Data for all participants will be assessed to determine if participants meet the criteria for inclusion in each analysis population prior to unblinding and releasing the database and classifications will be documented per standard operating procedures.

Table 2. Analysis Sets

Population	Description
Full analysis set	The full analysis set includes all enrolled participants. "Enrolled" means a participant's, or their legally authorized representative's, agreement to participate in a clinical study following completion of the informed consent process. Potential participants who are screened for the purpose of determining eligibility for the study, but do not participate in the study, are not considered enrolled, unless otherwise specified by the protocol.
Safety analysis set	The safety analysis set includes all enrolled participants who receive at least one dose of study intervention. Unless otherwise specified the safety analysis set will be the default analysis set used for all analyses.
Per protocol analysis set (Evaluable for MTD)	The per protocol analysis set includes all enrolled participants who had at least one dose of study treatment and either experienced DLT or do not have major treatment deviations during the DLT observation period. To be DLT evaluable, a participant must have received at least 75% of their planned doses in each cycle for the first two cycles (i.e., ≥ 11 doses received in each of the first two cycles) and has received all scheduled safety assessments during the DLT window.
Modified Intent to Treat (mITT)	The modified intent to treat (mITT) is the analysis population that will follow the ITT principle and include participants receiving at least 1 dose of study medication with baseline assessment and at least 1 post baseline assessment, disease progression, or death before the first tumor assessment. The mITT population may be used for interim analysis and conference presentations when the study is still ongoing.
PK analysis sets	The PK parameter analysis population is defined as all enrolled participants treated who do not have protocol deviations influencing PK assessment, and have sufficient information to estimate at least 1 of the PK parameters of interest.

Population	Description

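### The minimum at the MTD is 6 DLT-evaluable participants in the synopsis and Protocol 9.2.1 but 6 treated in the stopping rule (Protocol 9.4.1.1, SAP 5.1), and the two need reconciling

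*Protocol*

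**What the plan says.** **The minimum at the MTD.** The protocol synopsis says that for the dose estimated to be the MTD, "a minimum of 6 DLT evaluable participants will be treated at this dose". Protocol 9.2.1 says "a minimum of 6 evaluable participants will be treated at this dose"; the same paragraph speaks of participants evaluable for DLT, so the meaning is the same.

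**The stopping rule.** Protocol 9.4.1.1 requires that "At least 6 participants have been treated at the recommended MTD/RP2D", together with one of two further conditions: a posterior probability of target toxicity of at least 50%, or "A minimum of 15 participants have been treated in the trial". SAP 5.1 repeats this rule in the same words. The SAP text available contains no minimum of 6 evaluable.

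**The analysis set.** Protocol 9.4.1 states: "Determination of MTD will be performed using per protocol analysis set (evaluable for MTD". SAP 6.1.1 uses the same set for DLTs.

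**Who is evaluable.** Under Protocol 4.3.3, a participant without a DLT is evaluable only if he or she "receives 2 doses of the study intervention during Cycle 1 and has received all scheduled safety assessments during the DLT window". On replacement it says: "If a participant fails to meet these criteria, he/she may be replaced". SAP 6.1.1 also makes replacement optional. SAP Section 4 (Table 2) gives a different definition: "To be DLT evaluable, a participant must have received at least 75% of their planned doses in each cycle for the first two cycles", which it spells out as at least 11 doses in each of those cycles.

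**The concern.** A participant who leaves before the second Cycle 1 dose, or misses a scheduled safety assessment, without a DLT is treated but not evaluable. That person counts towards the 6 in the stopping rule and then drops out of the MTD analysis. The count that permits stopping and the data that support the decision come from different populations.

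The floor matters because of the second stopping condition. Part 1 expects 14 to 22 participants, so 15 treated will often be reached. Escalation may then stop without the 50% posterior condition, and the count of 6 is the only minimum in 9.4.1.1 on the amount of data at the chosen dose. That dose goes on to 60–90 expansion participants, and to as many as 90 + 60 = 150 if the two optional cohorts open.

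**Working it through.** **1. The plan's own figure.** The minimum of 6 is a design choice. The documents available give no formula or operating characteristics for it, so there is nothing to reproduce.

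**2. Passages side by side.**

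| Place | Minimum at the MTD | Unit counted |
|---|---|---|
| Protocol synopsis | 6 | DLT-evaluable |
| Protocol 9.2.1 | 6 | evaluable |
| Protocol 9.4.1.1 | 6 | treated |
| SAP 5.1 | 6 | treated |

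Six evaluable implies six treated, but not the reverse. All four statements can be satisfied together, and only the first two guarantee 6 evaluable.

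**3. How often 6 treated would give fewer than 6 evaluable.** The documents give no non-evaluable rate, so q is an assumption, shown as a range. Assume also that exactly 6 are treated, nobody is replaced, and participants are independent.

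- P(fewer than 6 evaluable) = 1 − (1 − q)^6
- P(4 or fewer evaluable) = 1 − (1 − q)^6 − 6q(1 − q)^5

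| q (assumed) | Fewer than 6 evaluable | 4 or fewer evaluable |
|---|---|---|
| 5% | 1 − 0.95^6 = 26.5% | 3.3% |
| 10% | 1 − 0.90^6 = 46.9% | 11.4% |
| 15% | 1 − 0.85^6 = 62.3% | 22.4% |
| 20% | 1 − 0.80^6 = 73.8% | 34.5% |

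Here q is the rate over all treated participants. Under Protocol 4.3.3 anyone with a DLT is evaluable, so the shortfall can arise only among those without one.

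**4. What a lost participant means for the data at that dose alone.** Take a true DLT rate p = 0.33, the overdosing boundary in Protocol 9.4.1. P(at most 1 DLT) = (1 − p)^n + np(1 − p)^(n−1), which is 35.8% for n = 6, 46.8% for n = 5 and 59.9% for n = 4. This is not the plan's inference, because the Bayesian logistic model also uses DLT data from other doses. No posterior was computed.

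**5. The number to treat if 6 evaluable are required.** Rounding 6/(1 − q) up gives 7 at q = 5% (6.3) or 10% (6.7), and 8 at 15% (7.1) or 20% (7.5). These are expectations, not guarantees. With 8 treated, P(fewer than 6 evaluable) = 1 − Σ C(8,k) q^k (1 − q)^(8−k) over k = 0 to 2, which is 3.8% at q = 10% and 20.3% at q = 20%.

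**6. Whether the SAP definition can be used.** Dosing on Days 1 and 15 of a 28-day cycle gives 2 doses per cycle, so 11 per cycle cannot be reached. Two cycles also span 2 × 28 = 56 days, against a 28-day DLT window.

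**The case against.** The strongest reply is that 9.4.1.1 says when escalation stops and does not cancel the separate minimum in the synopsis and 9.2.1. Both are floors and can be met together, so the protocol read as a whole still requires 6 evaluable at the MTD. This stands. A reader might infer that the plan allows the MTD to be declared on fewer evaluable participants than promised. The documents do not support that: it would require setting aside two protocol statements that remain in force. The SAP nowhere says that it lowers the minimum, and Protocol Section 9 says that major changes to primary endpoint analyses will also be reflected in a protocol amendment.

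It is also fair that non-evaluable participants never enter the MTD analysis, that they may be replaced, and that the dose level review can repeat or expand a cohort (Protocol 9.6). The probabilities above depend on an assumed rate, exactly 6 treated and no replacement, whereas the rule says at least 6. The single-dose figures do not describe the model's decision.

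None of this removes the mismatch. Restricting the analysis set does not turn 6 treated into 6 evaluable, and replacement is discretionary. Someone working from the Stopping Criteria section or from the SAP alone would not find the stricter requirement.

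**Conclusion.** The documents state the minimum information at the MTD in two incompatible units, and the passages that govern stopping use the weaker one. A shortfall arises only if 9.4.1.1 or SAP 5.1 is applied on its own. In that case, with exactly 6 treated and no replacement, the chance of fewer than 6 evaluable is about 27% to 74% for an assumed non-evaluable rate of 5% to 20%.

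The wording mismatch is certain; the size is illustrative. A reader might also infer that the RP2D would be materially less reliable. That has not been shown, because the effect of 5 rather than 6 evaluable participants on a model that borrows across doses was not computed. The point is worth correcting because it concerns a decision threshold, and the correction asks for nothing beyond what the protocol already promises.

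**What to change.** 1. Reconcile Protocol 9.4.1.1 and SAP 5.1 with the synopsis and 9.2.1, so that the stopping rule itself requires at least 6 treated and DLT-evaluable participants at the recommended MTD/RP2D.
2. Tie that term to a single cited definition. SAP Section 4 (Table 2), Protocol 4.3.3 and the Day 1 and Day 15 schedule must be reconciled in the same edit. If *DLT-evaluable* is added to SAP 5.1 while the SAP's 11-dose condition stands, participants without a DLT could not satisfy it.
3. State whether the condition of 15 participants treated in the trial also means evaluable.

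The cost is wording edits in the protocol and SAP, plus probably one or two replacements at the MTD, which the plan already permits. More will occasionally be needed, as step 5 of the working shows.
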